### **Analytic Plan**

#### **Specific Aims: WSWS-2 and WSWS-2BR Validation**

Psychometric analyses of the 18 item pool will be conducted to validate a full and brief version (6 items) of the WSWS2 in this sample of medicated and unmedicated smokers. The aims include clarifying the dimensional structure and the best-performing items to construct the final scales. Subscales will be evaluated with respect to internal consistency (e.g., Cronbach's alpha  $\geq .8$ ), item-analysis (response distributions, item-to-total correlations, IRT analyses), and confirmatory factor analyses (CFA) and measurement invariance (e.g., across at least 2 post-TQD time points).

Concurrent, discriminant, and predictive validity will be considered in evaluating and constructing the final scale. The WSWS2-L should demonstrate meaningful relations with measures of tobacco dependence (WISDM-PDM, FTCD, time to first cigarette), other published withdrawal scales (Minnesota Withdrawal Scale), and prediction of cessation outcomes (e.g., time to lapse/relapse, survival analyses). In analyses predicting cessation outcomes both pre-post increase in withdrawal symptoms and post-TQD symptoms per se will be used in prediction models. In addition, such models will be tested with and without (primary) covariates (gender, and race). The WSWS2-L should demonstrate a characteristic time-course of a withdrawal syndrome including sensitivity to abstinence (rise over first 12-24 hours and 2-4 days) and decrease over time following a peak in post-TQD. The time course will be examined with growth curve models that evaluate different trajectory components (i.e., linear, quadratic) with time

varying covariates for smoking lapse occurrence, exposure to temptation events, dependence level. The WSWS2-L should also be sensitive to medication use (e.g., decrease with C-NRT). This will be tested by determining the effects of C-NRT during Cessation on WSWS2-L scores versus precessation and unmedicated cessation levels. The WSWS2-L will be correlated with variables that assess relevant person factors such as affective disorder, distress tolerance, and the various measures of tobacco dependence.

We will conduct parallel set of psychometric and validation analyses of the WSWS2-B as we do with the WSWS2-L, except when not possible due to constraints placed on single-item subscales (e.g., subscale internal consistency, CFA).

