We will examine sensitivity to pharmacotherapy (nicotine patch + mini lozenge), which is hypothesized to decrease withdrawal severity. We will calculate residualized change scores (adjusting for pre-quit baseline) to quantify the change in WSWS2 total scale and subscale scores after 1 week of pharmacotherapy (Visit 3 scores, TQD +2w) relative to immediately prior to initiating pharmacotherapy (Visit 2 scores, TQD +1w) and separately, relative to a stable pre-quit baseline (Mean scores: Visit 1, Call 1, Call 2). We will examine these residualized change scores using GLMs to test whether the change significantly differs from zero and the corresponding effect size. We will examine unadjusted models as well as models controlling for medication dose (e.g., patch 7mg vs 14mg) and medication adherence. A valid assessment of withdrawal severity should be sensitive to decreases in symptoms following pharmacotherapy use.

We will conduct similar analyses with regard to the MTWS-R forms.

*Withdrawal Scale Comparison:*

As noted above, we will conduct parallel psychometric and validation analyses for the WSWS2-L, WSWS2-B, and MTWS-R, except when not possible due to constraints placed on single item-subscales (e.g., subscale internal consistency, CFA).

*Idiographic Examination of Withdrawal Waveforms & Prediction of Withdrawal Severity:*

We will examine plots of individual waveforms of withdrawal scores for the WSWS2 forms and subscales and the MTWS-R in order to reveal individual variation in withdrawal profiles over the pre-TQD and post-TQD assessment periods (e.g., peak, trajectory, average, variability, duration). Related to this, changes in symptom volatility and associations with episodic events (e.g., stressor occurrence, cue exposure) will also be examined in the pre- and post-TQD periods using piecewise linear models. The intent is to determine sensitivity to such events and to determine whether such sensitivity changes from pre- to post-TQD. Additionally, we will examine baseline factors (e.g., demographics, alcohol/cannabis use, chronic pain, anhedonia, anxiety/depression/stress, distress tolerance) that are most strongly associated with withdrawal severity during the pre-TQD and post-TQD periods.

*Craving Construct Exploration:*

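### The Visit 2 to Visit 3 change cannot show sensitivity to C-NRT, because in this one-group trial it mixes medication with time since quitting

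*SAP*

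**What the plan says.** The SAP section Sensitivity to Pharmacotherapy calculates residualized change scores, adjusted for pre-quit baseline, "after 1 week of pharmacotherapy (Visit 3 scores, TQD +2w) relative to immediately prior to initiating pharmacotherapy (Visit 2 scores, TQD +1w"). A second contrast takes Visit 3 "relative to a stable pre-quit baseline (Mean scores: Visit 1, Call 1, Call 2"). Both are examined "using GLMs to test whether the change significantly differs from zero and the corresponding effect size". Unadjusted models are planned, and also "models controlling for medication dose (e.g., patch 7mg vs 14mg) and medication adherence". The section then gives its criterion: "A valid assessment of withdrawal severity should be sensitive to decreases in symptoms following pharmacotherapy use". Similar analyses follow for the MTWS-R, and Withdrawal Scale Comparison makes the psychometric and validation analyses parallel across WSWS2-L, WSWS2-B and MTWS-R.

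The SAP Study Overview describes one group. The protocol (Smoking Cessation, Pharmacotherapy) has all participants told to begin C-NRT at TQD+8, and SAP Table 3 places the start on the day after Visit 2.

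The protocol's Analytic Plan expects the scale to show "sensitivity to abstinence (rise over first 12-24 hours and 2-4 days) and decrease over time following a peak in post-TQD". It lists a decrease with C-NRT as a separate expectation: "This will be tested by determining the effects of C-NRT during Cessation on WSWS2-L scores versus precessation and unmedicated cessation levels".

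**The concern.** The protocol names two reasons for scores to fall in the second week after quitting: the natural course of withdrawal after its peak, and C-NRT. The SAP's contrast responds to either, yet its heading and criterion credit C-NRT. A scale that follows nothing but days since quitting could satisfy the criterion.

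The error can also run the other way. In the full sample, participants who smoked before dispensing and stopped once on C-NRT could show a rise, so the absence of a fall is not clear evidence against a scale.

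At stake is one validity property among several. It is applied to all three instruments, so it feeds the Aim 2 comparison of scales.

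**Working it through.** The documents give no sample size, alpha or effect size for this analysis, so there is no planned figure to reproduce. The first two steps need no assumed numbers.

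**1. Can time and drug be separated at the planned visits?** Let *a* be the level, *b* the change per day since quitting and *c* the C-NRT effect.

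- Visit 2 (day 7, unmedicated): *a* + 7*b*
- Visit 3 (day 14, medicated): *a* + 14*b* + *c*
- Difference: 7*b* + *c*

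The design matrix with rows (1, 7, 0) and (1, 14, 1) has rank 2 for three unknowns. A mean fall of 0.40 fits *c* = 0 with 7*b* = −0.40, or *c* = −0.40 with *b* = 0, or any split between them.

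The pre-quit contrast adds a third unknown, the abstinence effect *q*. Visit 3 minus baseline is *q* + 14*b* + *c*, and Visit 2 minus baseline is *q* + 7*b*. Subtracting returns 7*b* + *c*, so nothing is gained.

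**2. Does another planned analysis separate them?**

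| Planned analysis | Why it does not |
|---|---|
| Patch dose covariate (SAP, Sensitivity to Pharmacotherapy) | Dose is set by smoking or nicotine use in the 3 days before distribution (protocol, Pharmacotherapy) |
| Adherence covariate (same SAP section) | Not aliased with time, but self-selected, and use may be altered after side effects |
| Piecewise trajectory model (SAP, Sensitivity to Abstinence) | Ends at week 1, before C-NRT |
| Growth curves (protocol, Analytic Plan) | State no end day; covariates are "varying covariates for smoking lapse occurrence, exposure to temptation events, dependence level", with no C-NRT term |
| C-NRT comparison (protocol, Analytic Plan) | Names no time term |
| Abstinent subsets and smoking covariate (SAP, Sensitivity Analyses) | Address smoking, not elapsed time |
| Waveform analyses (SAP); time-varying effects models (protocol, Exploratory Analyses) | The models target events such as stressors and cues, not C-NRT onset |

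**3. How often could a purely natural fall pass?** This is illustration only. Assume zero drug effect and a two-sided one-sample t test at .05. With a natural fall of *d* SDs of the change score, the noncentrality is λ = *d*√*n*. The rejection probability is 1 − F(t*; *n*−1, λ) + F(−t*; *n*−1, λ), where F is the noncentral t distribution and t* its .975 critical value under no change. For example, *d* = 0.2 and *n* = 200 give λ = 0.2 × 14.14 = 2.83 and probability .804.

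| *n* | *d* = 0.02 | 0.05 | 0.1 | 0.2 | 0.3 |
|---|---|---|---|---|---|
| 150 (assumed) | .057 | .093 | .229 | .682 | .955 |
| 200 (assumed) | .059 | .108 | .291 | .804 | .988 |
| 232 (all enrolled) | .061 | .118 | .329 | .859 | .995 |

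To tie *d* to a time course, assume exponential decay with time constant τ days from a day-3 elevation E. The day 7 to day 14 fall is E(e^(−4/τ) − e^(−11/τ)). Take an assumed SD of change of 0.85 and *n* = 200. For τ = 7 and E = 0.5, the fall is 0.5 × (0.565 − 0.208) = 0.18, or 0.21 SD. The probability of a significant drop is then:

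| τ (days) | E = 0.25 | E = 0.5 |
|---|---|---|
| 1 | .030 | .035 |
| 1.5 | .047 | .082 |
| 2 | .078 | .192 |
| 3 | .165 | .506 |
| 5 | .289 | .802 |
| 7 | .316 | .842 |
| 10 | .288 | .799 |
| 14 | .232 | .689 |

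If withdrawal has almost resolved by day 7, the test stays near its nominal level. If it is still resolving, the error is large.

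**4. What is being tested?** Residuals from a regression with an intercept average zero by construction. In a simulated sample of 200 with mean change −0.126, the residuals of change on baseline averaged zero to machine precision, while the intercept with baseline centred returned −0.126. Read literally, the planned test is empty. The baseline-centred intercept is the quantity that can be tested.

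**The case against.** The criterion sentence describes a sequence in time and a necessary condition. The SAP nowhere says a fall proves a drug effect or is enough for validity. That is so, but the section heading, and the protocol's reference to C-NRT effects, assign the fall to medication.

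The trial is about scale validity, not efficacy. A natural fall would still show a scale following declining withdrawal, and the other validity analyses do not rest on this contrast. This stands, and it limits the weight of the point. The illustration in step 3 also says nothing about what happened in this trial; the case rests on steps 1 and 2.

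Reading *residualized change* as a baseline-adjusted mean change is the natural interpretation. Agreed; it needs one line to say so.

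The strongest objection is that the trial holds more information than two visits. EMA runs to TQD+14, and start days will vary somewhat because medication is mailed when Visit 2 is held by phone. Daily data with a break at the C-NRT start are identifiable (rank 3 of 3 with a linear trend). The SAP does not plan such a model, however, and its answer depends on the assumed shape of natural decline. All the following simulations had zero drug effect:

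- Under exponential decay (N = 232, daily data from TQD to +14, time constants 5, 10 and 20 days), a quadratic break model gave false drops in 0%, 1% and 2% of runs. The two-visit test gave 74%, 95% and 84%.
- Under a steep logistic decline centred on day 8 (N = 200, evening data from TQD+4 to +14, elevation 0.5), a step model gave false drops in 54% of runs, or 38% with staggered starts.
- With fast exponential decay (constants 1 to 1.5 days) from a 1-point elevation, the step model gave false rises in 48%.

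The last two are near worst case. At a 0.25-point elevation the logistic false drops were about 17%; at 0.25 to 0.5 points the fast-decay false rises were about 7% to 15%. The conclusion remains that EMA can separate the effects only if the decline curve is known, and the documents do not give it.

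**Conclusion.** The concern holds. The mean Visit 2 to Visit 3 change cannot distinguish C-NRT from time since quitting, and no analysis specified in either document combines a C-NRT term with a time trend for this question. That follows from the one-group design and the common start instruction.

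The size of the error is unknown. Over the assumed inputs, the chance that a purely natural course gives a significant result runs from about the nominal level to above .99, depending on how much decline remains after day 7. The test alpha, the numbers attending both visits, the SD of change and the decay shape are all assumptions.

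The section should be changed, but the point touches one validity property and leaves the remaining validation work intact.

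**What to change.** 1. In SAP, Sensitivity to Pharmacotherapy, describe the Visit 2 to Visit 3 change for WSWS2-L, WSWS2-B and MTWS-R as uncontrolled change during the first week of C-NRT that cannot be separated from time since quitting. State that a decrease on its own does not count as evidence of pharmacotherapy sensitivity.
2. State that the tested quantity is the baseline-adjusted mean change, meaning the intercept of the change model with baseline centred.
3. Disclose the change as made after the December 8, 2022 registration.

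The cost is SAP wording, plus giving up the claim that this contrast demonstrates pharmacotherapy sensitivity. No new data are needed.

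An EMA step model is not needed for this correction. If the investigators run one, it should be labelled exploratory, with the assumed decline curve stated and neither a significant nor a null step treated as conclusive. It could not serve the Aim 2 comparison, because the MTWS-R is scheduled at calls and visits and not in EMA.

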## Study Overview

Adults who smoked cigarettes daily and desired to quit smoking enrolled in this study (N=232). This treatment-delay, one-group clinical trial was intended to validate and/or enhance the assessment of tobacco withdrawal amongst participants who try to quit smoking without using

medication early in the course of their quit attempt. Participants attempted to quit smoking and were instructed not to use any smoking cessation pharmacotherapy during the first week of their quit attempt. They initiated pharmacotherapy 1 week past the target quit day (TQD) and continued pharmacotherapy through 9 weeks past the TQD. This will allow for the examination of withdrawal symptoms for 1-week post-TQD in participants who are not using pharmacotherapy. Participants received 8 weeks of combination nicotine replacement therapy (C-NRT: nicotine patch + nicotine mini-lozenge) starting 1 week past the TQD. Participants received 4 counseling sessions (1 pre-TQD, 3 post-TQD) that conform to the US PHS Clinical Practice Guideline recommendations (Fiore et al., 2008). Participants completed 4 weeks of ecological momentary assessment (EMA) including a 2-week baseline (starting TQD -14d) and 2-week post-TQD (1-week un-medicated, 1-week using C-NRT). Enrolled participants completed an Orientation Phase, Pre-cessation Phase, Cessation Phase, and Follow-up Phase (Visit 4 only if self-reported 7d point prevalence abstinence). See Tables 1-3 below for timing of assessment and study activities.

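### The test of sensitivity to C-NRT compares residualized change scores with zero, but in the usual sense those scores average zero by construction, so no fall in withdrawal can be detected.

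*SAP*

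**What the plan says.** The SAP section Sensitivity to Pharmacotherapy works in two steps. First it builds a score: "We will calculate residualized change scores (adjusting for pre-quit baseline) to quantify the change in WSWS2 total scale and subscale scores". There are two contrasts, Visit 3 against Visit 2, and Visit 3 against the mean of Visit 1, Call 1 and Call 2. Then it tests the score: "We will examine these residualized change scores using GLMs to test whether the change significantly differs from zero", with an effect size. The covariates come next: "We will examine unadjusted models as well as models controlling for medication dose (e.g., patch 7mg vs 14mg) and medication adherence". The same analyses are to be run for the MTWS-R.

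Neither this section nor any other gives the regression behind the scores, a centring rule or an intercept rule.

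The protocol's Analytic Plan describes the same question as a comparison of score levels: "This will be tested by determining the effects of C-NRT during Cessation on WSWS2-L scores versus precessation and unmedicated cessation levels". Both documents treat a fall in scores on C-NRT as something a valid withdrawal scale should show.

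**The concern.** Residualized change scores rank people against what their own earlier scores predict. They suit questions about who changed more, or about differences between arms. The SAP's Study Overview describes a single group ("This treatment-delay, one-group clinical trial was intended to validate and/or enhance the assessment of tobacco withdrawal"), so there is no second arm. The only quantity left to compare with zero is the overall mean, and residualizing removes it.

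Two harms follow. In the unadjusted model the output would be exactly zero. That would probably be noticed, and the method would then be changed after the data had been seen, which is what registering this SAP was meant to prevent. In the adjusted models the output can look like an ordinary estimate and p value while carrying no information about mean change, so an error there is easier to miss.

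No other planned analysis fills the gap with an inferential test of mean change from Visit 2 to Visit 3. The piecewise models under Sensitivity to Abstinence stop at one week after the quit day, before C-NRT starts, and the waveform plots are descriptive.

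**Working it through.** The plan gives no sample size, power or effect size for this test, so there is no figure to reproduce. The central point is algebra. The simulations only show what it looks like in data.

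**Inputs from the documents.** Visits 2 and 3, and the pre-quit baseline B (mean of Visit 1, Call 1, Call 2), come from the SAP section on pharmacotherapy. N = 232 enrolled comes from the SAP Study Overview and is an upper bound for Visits 2 and 3.

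**Assumed, not in the documents.** Score SD 0.8; correlation 0.6 between occasions; half on each patch dose; adherence scored 0 to 1 with mean 0.67; two-sided alpha 0.05; 1,000 runs per setting.

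**Step 1: unadjusted model.** Let D = V3 - V2. Fit D = a + bB by least squares and take the residual e = D - a - bB. Since a = mean(D) - b·mean(B),

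mean(e) = mean(D) - a - b·mean(B) = 0.

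The one-sample statistic is 0/SE = 0, so p = 1. The same holds for V3 regressed on V2 and B, for V3 regressed on B (the pre-quit contrast), and for the difference between two residuals when each visit is fitted separately. In simulation, with all four versions, N of 150, 200 and 232 and true changes of 0, -0.3 and -1.0, the largest absolute mean was 5e-15 and the smallest p value was 1.000.

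**Step 2: adjusted models.** Add a constant δ to every Visit 3 score. Then a rises by δ and every e is unchanged. Anything computed from e, including intercept, dose coefficient, adherence coefficient and p values, is therefore also unchanged. Fitting e = g0 + g1·dose + g2·adherence gives

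g0 = 0 - g1·mean(dose) - g2·mean(adherence).

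With centred covariates g0 is again exactly 0. With uncentred covariates it reflects only differential change. If change differs by -0.8 from no adherence to full adherence and dose has no effect, g0 ≈ 0.8 × 0.67 = +0.54. The simulated average was +0.53, which has the sign of an increase.

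**Step 3: one simulated dataset (N = 232), shifting every Visit 3 score.**

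| Shift added | Uncentred adjusted intercept on residuals | Raw change, all covariates centred (95% CI) |
|---|---|---|
| 0 | 0.682, p = 0.0012 | -0.020 (-0.119 to 0.078) |
| -0.3 | 0.682, p = 0.0012 | -0.320 (-0.419 to -0.222) |
| -1.0 | 0.682, p = 0.0012 | -1.020 (-1.119 to -0.922) |

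**Step 4: repeated runs (N = 232).** With the -0.8 adherence slope, the uncentred intercept was significant in 81.7% of runs, identically at true changes of 0, -0.3 and -1.0. With no adherence effect it rejected in 5.0% at all three. The raw-change model with centred covariates recovered -0.300 and -1.000, rejecting in 100% of runs at both and in 4-5% at zero change.

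**Step 5: is the raw-change test adequate?** SD of change = SD × √(2(1 - r)). In the worst case tried, SD 1.2 and r = 0.3, this is 1.2 × √1.4 = 1.42. At N = 200, SE = 1.42/√200 = 0.100, and a change of -0.3 gives a noncentrality of 2.99 and power of 84.5%. Over SD 0.6 to 1.2 and r 0.3 to 0.8, power runs from there to about 100%.

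**The case against.** The best counter-argument is about reading. The SAP says the scores quantify change at Visit 3 relative to Visit 2, adjusted for baseline, and asks for an effect size. That could describe a baseline-adjusted raw change, which is a sound test if baseline is centred. Some less usual constructions are also not degenerate. If Visit 2 and Visit 3 are pooled in one regression on baseline and the residuals differenced, the result is V3 - V2 exactly. If Visit 2 is predicted from baseline and that prediction is subtracted from Visit 3, the mean is mean(V3) - mean(V2). This stands as a statement of what the authors may have meant. It does not rescue the text: these are tests of raw or near-raw mean change, and the SAP specifies none of them. Even the favourable reading needs the equation, because with an uncentred baseline the intercept is the expected change at a baseline score of zero.

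The second objection is to the 81.7%, and it is largely right. The figure needs an uncentred adherence term, a slope of -0.8 (a full assumed SD) and a particular spread of adherence. Other spreads with the same mean gave about 66% to 95%. With a slope of -0.4 and a Beta(2,1) adherence distribution, the rate was 29-43% for N of 150 to 232. With a 0/1 dose term as the only covariate and no dose effect, it was 0.4-1.4%. The rate is illustrative. What does not depend on these choices is that the result is identical at every true mean change.

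Third, the harm is bounded. Raw scores are kept at every visit, the protocol already describes a comparison of levels, and this is one validation analysis among many. That argues against a higher severity, not against the correction.

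**Conclusion.** The concern holds. On the ordinary meaning of residualized change, the planned test cannot show a mean fall in withdrawal after C-NRT starts, for either contrast or either scale. The zero mean and the invariance to a uniform shift are identities and rest on no assumption about the data. They do require residuals from a fit with an intercept, tested in the same sample. In a subset such as abstainers, residuals from the full-sample fit could have a non-zero mean, but it would show only departure from the full-sample average.

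The rejection rates, intercept sizes and power rest on the assumed SD, correlation and adherence pattern. The defect should be fixed before analysis. It affects the pharmacotherapy criterion and that part of the Aim 2 comparison with the MTWS-R. It leaves the Aim 1 abstinence test untouched, and residualized scores remain usable for asking whether dose or adherence goes with more or less change.

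**What to change.** Replace the residualized-score test with a stated model:

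- **Outcome:** raw within-person change, Visit 3 minus Visit 2; separately, Visit 3 minus the mean of Visit 1, Call 1 and Call 2.
- **Model:** linear, with pre-quit baseline centred at its grand mean. In the adjusted versions, centre dose and adherence too. A repeated-measures model with a visit contrast is an equivalent choice.
- **Test and report:** the intercept (or visit contrast), with estimate, 95% CI and standardized effect, for both WSWS2 forms and the MTWS-R.
- **Residualized scores:** keep only for correlating change with other variables.

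Also add one sentence on interpretation. The protocol itself expects scores to "decrease over time following a peak in post-TQD", so in a one-group design a fall from Visit 2 to Visit 3 includes that natural decline and does not by itself isolate the effect of C-NRT. This is a limit on what the corrected test can claim, separate from the defect above.

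The cost is a few sentences of SAP wording. No new data are needed, and the change brings the SAP back to the comparison of levels in the protocol.
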